5.2. Participant Disposition

The number of participants screened, the number of participants screen failed, primary reason for screen failure and the number of participants re-screened will be presented. In addition, the number of participants who were randomized will be given.

The number of participants included in the analysis sets by intervention group will be presented. Percentages will be based on the number of participants in the RAS. In addition, the distribution of participants by region, country and site ID will be presented for the Full Analysis Set.

The number and frequency of participants in the following disposition categories will be summarized by the intervention group based on the Full Analysis Set:

- Participants who received study intervention
- Participants who completed the study intervention through Week 48
- Participants discontinuing study intervention prior to Week 48 and reasons for discontinuation
- Participants discontinuing study intervention prior to Week 156 and reasons for discontinuation
- Participants who terminated study participation prior to Week 156 and reasons for termination

A listing of participants who prematurely discontinued study intervention or prematurely discontinued the study and the primary reason for discontinuation will be presented. The listing will identify the visits completed and when the study intervention or study was discontinued.

Listings of participants will be provided for the following categories:

- Participants who discontinued study intervention prior to Week 48
- Participants who terminated study participation
- Participants who were randomized yet did not receive study intervention
- Participants who were unblinded prior to Week 48

Study assessment of compliance will be summarized and listed by randomized treatment group. This will include the number of participants who missed at least one scheduled CDAI assessment, at least one scheduled endoscopy assessment, or at least one missed study agent administration due to any reason or due to COVID-19-related events.

5.3. Primary Endpoint(s) Analysis

5.3.1. Definition of Endpoint

The primary endpoint is endoscopic recurrence prior to or at Week 48 as defined by modified Rutgeerts score \geq i2a in the neo-terminal ileum, anastomotic site, or its equivalent elsewhere in the GI tract (eg, colonic ulceration).

Rutgeerts score

Score	Endoscopic Findings
i0	No lesions
i1	< 5 aphthous lesions
i2	> 5 aphthous lesions with normal mucosa between the lesions or skip areas of larger lesions or lesions confined to the ileocolonic anastomosis (ie, < 1 cm in length)
i2a	Lesions confined to the ileocolonic anastomosis (including anastomotic stenosis)
i2b	More than 5 aphthous ulcers or larger lesions, with normal mucosa in-between, in the neoterminal ileum (with or without anastomotic lesions)
i3	Diffuse aphthous ileitis with diffusely inflamed mucosa
i4	Large ulcers with diffuse mucosal inflammation or nodules or stenosis in the neoterminal ileum

5.3.2. Estimand

5.3.2.1. Primary Estimand

An estimand is a precise definition of the primary targeted treatment effect defined by the following 5 attributes: Study Intervention, population, variable (endpoint), intercurrent events (ICEs) and corresponding strategies, and population-level summary.

Primary Trial Objective: To evaluate the efficacy of guselkumab treatment prior to or at Week 48 compared with placebo in preventing endoscopic recurrence of CD in participants after surgery.

Estimand Scientific Question of Interest: What is the proportion of participants developing endoscopic recurrence prior to or at Week 48, and thus considered to have benefited from guselkumab versus placebo?

Study intervention:

- Experimental: Guselkumab ^{CCI} at Week 0 and then ^{CCI} at Week 8, then ^{CCI} thereafter through the end of the total study period.
- Control: Matched placebo CCI at Weeks 0 and 8 and then CCI thereafter through the end of the total study period.

Population: Participants with recent (<49 days) qualifying surgery and no evidence of active Crohn's disease postoperatively.

Variable: A binary recurrence variable (recurrence/no recurrence) where recurrence is defined as Endoscopic Recurrence prior to or at Week 48 (as defined by modified Rutgeerts score greater than or equal to i2a in the neo-terminal ileum, anastomotic site, or its equivalent elsewhere in the GI tract (eg, colonic ulceration)) or experiencing intercurrent events (ICEs) 1-4 presented below.

Summary Measure (Population-level summary): Difference in proportions of the binary recurrence variable of endoscopic recurrence, as described above, between guselkumab group and the placebo group.

Intercurrent events and their corresponding strategies:

The ICEs considered for this study are listed in Table 7:

Table 7:	Intercurrent Events and Corresponding Analysis Strategies for Endoscopic Recurrence prior to
	or at Week 48

Inte	ercurrent Events (between baseline and Week 48)	Analysis Strategy for Intercurrent Events
1. 2.	A CD-related surgery (with the exception of minor procedures such as drainage of a superficial abscess or seton placement, etc.) A prohibited change in CD medication	
3. 4.	Discontinuation of study intervention due to lack of efficacy or an AE of worsening CD Cross over to open-label guselkumab	
5. 6.	Discontinuation of study intervention due to COVID-19 related reasons (excluding COVID-19 infection) Discontinuation of study intervention due to reasons other than those in ICE 3 or 5	and any data observed after the associated ICE event will be used for the analysis

Abbreviation: AE=adverse event; CD=Crohn's disease; COVID-19= Coronavirus disease 2019; ICE=intercurrent event

20

Intercurrent events in categories 1-4 will be handled by the composite strategy. The composite strategy assesses the treatment effects not only based on the variable measurements, but also based on ICEs. This estimand acknowledges that having an ICE in categories 1-4 is an unfavorable outcome. For participants experiencing ICEs in category 5 and 6, the treatment policy strategy will be used and considers the occurrence of ICE category 5 and 6 is irrelevant in defining the treatment effect and so observed values of the variable will be used, if available, regardless of the occurrence of ICE category 5 and 6.

5.3.2.2. Supplementary Estimands for the Primary Endpoint

5.3.2.2.1. All ICEs Composite

In this supplementary estimand, all ICEs defined above for the primary estimand are addressed by the **composite strategy**. The supplementary estimand for the primary endpoint acknowledges that having an ICE is an unfavorable outcome. Besides the strategy change, other components of the supplementary estimand are the same as those for the primary estimand with the exception of the Variable, which is described as follows:

Supplementary Estimand of Endoscopic Recurrence prior to or at Week 48

Variable (endpoint): A binary recurrence variable (recurrence/no recurrence) where recurrence is defined as Endoscopic Recurrence prior to or at Week 48 (as defined by modified Rutgeerts score greater than or equal to i2a in the neo-terminal ileum, anastomotic site, or its equivalent elsewhere in the GI tract (eg, colonic ulceration)) or experiencing intercurrent events (ICEs) 1-6 presented in Table 7.

5.3.3. Analysis Methods

5.3.3.1. Estimator (Analysis) of the Primary Estimand

The analyses will be based on the Full Analysis Set (FAS), which includes all randomized participants. Participants will be analyzed according to the intervention group to which they were randomized regardless of the study intervention they actually received.

To compare the guselkumab versus placebo group for the primary endpoint, the Cochran Mantel Haenszel chi-square test (2-sided) will be used with stratification of clinical remission status at baseline (CDAI < 150, CDAI \ge 150), region (North America, Western Europe, rest of world) and number of prior surgeries (1 surgery versus > 1 surgery, with the qualifying surgery counting as 1 surgery). The study will be considered successful if the test of the primary endpoint is positive at the 0.05 significance level.

After accounting for the ICE strategies, missing data will be imputed by multiple imputation.

Multiple imputation will be used for imputing missing data under the assumption that the data are MAR. The analysis will impute the missing Rutgeerts score at Week 48 using the analysis method and ancillary variables as described in Table 8. The responses at Week 48 will be derived from the imputed datasets and combined for analysis.

Variable	MI specification	Analysis method/Summary statistics
Rutgeerts score at Week 48	Multiple imputation with monotone regression of total scores	 MIdataset1 (N=200, Seed=5748941) Imputation variables: Rutgeerts score at Week 48 Ancillary variables: Treatment group, and history of primary non-response to at least one approved ADT (Yes, No), clinical remission status at baseline (CDAI < 150, CDAI ≥ 150), region (North America, Western Europe, rest of world) and number of prior surgeries (1 surgery versus > 1 surgery, with the qualifying surgery counting as 1 surgery)

 Table 8:
 Multiple Imputation Methods for Rutgeerts Score at Week 48

The number and percentage of participants who experienced any ICE prior to Week 48 will be summarized by the type of ICE.

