1.2. Study Design

1.2.1. Overall Design

This is a Phase 3, multicenter, randomized, placebo-controlled, prospective double-blind study designed to evaluate the efficacy and safety of guselkumab in preventing the recurrence of active CD in patients who have recently undergone a surgical resection for CD. A diagram of the study design is provided in Section 1.2.2, Schema.

The target population is male or female participants (minimum age 18) with a diagnosis of CD who have a qualifying surgery (eg, ileocolonic resection) a maximum of 49 days before randomization. Participants will be excluded if they have a short segment of bowel affected (ie, less than 10 cm) for fibrostenotic disease and they had their first surgery more than 10 years after diagnosis of CD. There is no requirement that participants have failed prior biologics.

Participants will have a baseline CDAI <200 and will be eligible regardless of prior biologic use. Participants who are low risk for recurrent CD (ie, participants whose qualifying surgery was their first in >10 years since their diagnosis of CD and was performed for fibrostenotic stricturing disease involving <10 cm of the intestine) will be excluded. Participants must be able to undergo randomization no later than 49 days after surgery.

A target of approximately 370 participants will be enrolled from approximately 150 sites. The target population consists of participants with CD who have undergone a recent (\leq 49 days) ileocolonic resection with ileocolonic anastomosis for CD, without evidence of active disease postoperatively. Participants must not have had their qualifying surgery for the purpose of resecting known dysplasia.

Randomization will occur in a 1:1 ratio with participants receiving either:

- Arm 1 (Guselkumab): Guselkumab ^{CCI} at Week 0 and then ^{CCI} at Week 8, then ^{CCI} thereafter through the end of the total study period.
- Arm 2 (Placebo): Matched placebo ^{CCI} at Week 0 and then ^{CCI} thereafter through the end of the total study period.

Randomization will be stratified by clinical remission status at baseline (CDAI < 150, CDAI \geq 150), region (North America, Western Europe, rest of world) and number of prior surgeries (1 surgery versus > 1 surgery, with the qualifying surgery counting as 1 surgery).

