3. SAMPLE SIZE DETERMINATION

A sample size of 370 participants (185 participants assigned to guselkumab and 185 assigned to placebo) will allow to have at least 90% power to detect 20% differences between guselkumab (30%) and placebo (50%) for endoscopic recurrence rate (primary endpoint) at Week 48, assuming a 2-sided alpha level of 0.05.

This also will allow at least 90% power to detect 17% differences between guselkumab (37%) and placebo (20%) for clinical remission without disease recurrence at Week 48, assuming a 2-sided alpha level of 0.05. This also will allow 90% power to detect 10% differences between guselkumab (10%) and placebo (20%) for disease recurrence at the main database lock, all available follow-up of all participants will be used to examine disease recurrence at the time of the primary database lock.

Endoscopic Recurrence

Assumptions for endoscopic recurrence prior to or at Week 48 were based on previous studies, as described in Table 2.

Reference*	Endoscopic Recurrence definition	Sample Size	Placebo rate	Timepoint
		-		-
Regueiro 2016	Rutgeerts \geq i2	150	60%	76 weeks
Yamamoto 2007	Rutgeerts \geq i2	20	70%	52 weeks
Marteau 2006	Rutgeerts \geq i2	47	64%	24 weeks
Rutgeerts 2005	Rutgeerts \geq i2	33	78.8%	52 weeks
Hanauer 2004	Rutgeerts \geq i2	40	64%	104 weeks
Lochs 2000	Rutgeerts \geq i2	166	50%	72 weeks
Ewe 1999	Rutgeerts \geq i2	40	70%	52 weeks
Hellers 1999	Rutgeerts \geq i2	66	58%	52 weeks

Table 2:	Endoscopic	Recurrence,	Placebo	Group
----------	------------	-------------	---------	-------

* References are provided in the protocol.

Based on these data above, the endoscopic recurrence rates are assumed to be 50% for placebo and 30% for guselkumab.

To accommodate other potential scenarios, power was calculated based on different assumptions as listed in Table 3.

Event rate at Week 48 for endoscopic recurrence in placebo group	Event rate at Week 48 for endoscopic recurrence in guselkumab group	Difference to be detected	Power
50%	30%	20%	97.7%
50%	25%	25%	99.9%
50%	35%	15%	83.3%
45%	25%	20%	98.3%
40%	20%	20%	98.9%
60%	30%	30%	>99.9%

 Table 3:
 Power to Detect a Treatment Effect Based on Different Scenarios in Endoscopic Recurrence

Clinical Remission without Disease Recurrence

Based on data from PREVENT (20% for placebo, and 36.7 for Infliximab), the rates of clinical remission without disease recurrence are assumed to be 20% for placebo and 37% for guselkumab.

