Accrual time used here is 18 months, total time used here is 30 months. It is expected median follow-up time available at the time of, and thus incorporated in, the main database lock is approximately 18 months. Assuming non-uniform accrual pattern: 25% of participants will be enrolled in the first 6 months, 35% of participants will be enrolled in the next 6 months, and 40% will be enrolled in the last 6 months. Assuming dropout rate is 15% annually. Average duration of follow-up is expected to be approximately 20 months.

Analysis Sets	Description
Randomized	The randomized analysis set includes all participants who were
	randomized in the study.
Full Analysis Set (FAS)	All randomized participants.
	Participants in the FAS will be analyzed according to their randomized study intervention regardless of the study intervention they actually received.
Safety Analysis Set	All randomized participants who receive at least 1 dose of study intervention.
	Participants in the Safety Analysis Set will be analyzed according to the study intervention they actually received.
Pharmacokinetics Analysis Set	All randomized participants who receive at least 1 dose of study intervention and have at least one valid blood sample drawn postbaseline for PK analysis.
	Participants in the PK Analysis Set will be analyzed according to the study intervention they actually received.
Immunogenicity Analysis Set	All participants who received at least 1 dose of study intervention and have appropriate samples for anti-drug antibody detection.
	Participants in the Immunogenicity Analysis Set will be analyzed according to the study intervention they actually received.

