5.4.1.1. Definition of Endpoint(s)

Clinical remission without disease recurrence is a composite endpoint defined by the following:

- CDAI < 150 at Week 48 and
- No endoscopic recurrence as defined by Rutgeerts score < i2a by Week 48 and
- Have not experienced a disease recurrence as defined below

Disease recurrence is a composite endpoint defined by the following:

- A ≥ 70-point increase from baseline in CDAI score at beyond 8 weeks after randomization; and a CDAI score of ≥ 200 **and** evidence of endoscopic recurrence. Endoscopic recurrence is defined as a modified Rutgeerts score of ≥ i2a at the anastomotic site or its equivalent elsewhere in the GI tract, unless a stool test for C. difficile toxin or other enteric pathogen is positive
- In event of a positive test for enteric pathogen including C. difficile toxin, the underlying infection should be treated and if ileocolonoscopy has not yet been performed, it should only be done when the infection has resolved, and if disease recurrence threshold is still met
- OR initiation of a physician-prescribed corticosteroids, or an increase in the dose of steroids already being taken (by greater than 5 mg/day), for over one week for the treatment of CD and evidence of endoscopic recurrence as described above, unless a stool test for C. difficile toxin or other enteric pathogen is positive
- OR a new draining external fistula
- OR the reopening and draining of a previously existing external fistula
- OR developing a new internal fistula
- OR developing a new perianal abscess
- OR developing a new intra-abdominal abscess more than three months after the date of the index surgery

Participants who have confirmed endoscopic recurrence without disease recurrence at Week 24 or Week 48 and cross over to open-label guselkumab treatment will be censored at cross over for the time to disease recurrence endpoint.

Abdominal pain free at Week 48 is defined as abdominal pain (AP) score = 0 at Week 48

Time-to-recurrence of symptoms is defined as time to attaining an AP mean daily score >1 (and also >1 point higher than baseline) along with stool frequency (SF) mean daily score >3 (and also >3 higher per day than baseline) for 2 consecutive weeks through Week 48. Participants who cross over to open-label guselkumab treatment and do not have recurrence of symptoms will be censored at cross over for the time to recurrence of symptoms endpoint.

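### The imputation of the Rutgeerts grade and the abdominal pain score by continuous regression does not fit the endpoints derived from them: the effect is small for the primary endpoint and material for abdominal-pain-free at Week 48

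*SAP*

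**What the plan says.** **Primary endpoint.** SAP 5.3.3.1 applies the intercurrent event (ICE) rules and then fills in missing data under MAR: "The analysis will impute the missing Rutgeerts score at Week 48 using the analysis method and ancillary variables as described in Table 8". Table 8 names the method as "Multiple imputation with monotone regression of total scores", and the Week 48 response is derived from the completed datasets. SAP 5.3.1 lists the grades as i0, i1, i2, i2a, i2b, i3 and i4, with recurrence at i2a or above. No numeric coding is given.

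**AP-free.** SAP 5.4.1.3, Table 12, uses the same method for the Week 48 AP score. The endpoint in 5.4.1.1 is strict: "Abdominal pain free at Week 48 is defined as abdominal pain (AP) score = 0 at Week 48". No minimum, maximum or rounding unit is stated.

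**Related text.** For clinical remission without disease recurrence, AP-free and steroid-free remission, the narrative in 5.4.1.3 says that the missing Rutgeerts score is imputed, whereas Tables 11 to 13 impute CDAI or AP. Those three tables also list a baseline Rutgeerts score as a covariate. The protocol's Schedule of Activities has no ileocolonoscopy at screening or Week 0.

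**Status.** SAP Section 1 reports that four participants were enrolled, that the planned analyses no longer apply, and that they are retained for reference.

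**The concern.** The ordinary meaning of regression imputation for a score is a normal linear model that draws values on a continuous scale. Two things go wrong when a yes/no endpoint is cut from such draws.

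First, the Rutgeerts grade is an ordered classification and not a total. The analyst must choose a number for each grade (including whether i2a and i2b are separate steps) and choose whether to round before applying the threshold. Two statisticians following Table 8 could obtain different primary results.

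Second, AP-free has its threshold at the floor of the scale. A continuous draw equals 0 with probability zero, so the stated MAR imputation turns into non-responder imputation without saying so. AP-free is fourth of six in the testing order in 5.4.1.3, so a lost test there also closes the tests of time to recurrence of symptoms and steroid-free remission.

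**Working it through.** **Inputs from the documents.** 185 per arm, 1:1, two-sided 0.05; "the endoscopic recurrence rates are assumed to be 50% for placebo and 30% for guselkumab" (SAP Section 3). The only figure bearing on missing data is "Assuming dropout rate is 15% annually" (same section), which gives 1 − 0.85^(48/52) = 13.9% by Week 48. I use 15%, and 5% to 20% for AP.

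**Assumed inputs.** The documents give no grade distribution and no AP-free rate.
- Grade shares, placebo / guselkumab, all with true recurrence 50% / 30%:
  - A, codes 0–5: 25, 25, 15, 15, 12, 8 / 40, 30, 10, 10, 6, 4.
  - B, codes 0–5: 20, 30, 25, 20, 3, 2 / 35, 35, 15, 12, 2, 1.
  - C, codes 0–5: 45, 5, 5, 10, 20, 15 / 60, 10, 5, 5, 10, 10.
  - D, i2a and i2b merged, codes 0–4: 25, 25, 30, 12, 8 / 40, 30, 20, 6, 4.
- AP-free true rates 40% / 55%, with the remaining participants spread over AP values from 1/7 to 2.

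**Step 1: the plan's own figure.** Power = Φ[(|p1 − p2| − 1.96·s0)/s1], with s0 = √(2p̄(1 − p̄)/n) and s1 = √((p1(1 − p1) + p2(1 − p2))/n). For 50% v 30%, n = 185: s0 = 0.0509, s1 = 0.0499, z = 2.009, power 97.8%. The SAP states 97.7%, so it reproduces. This figure does not depend on the imputation model.

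**Step 2: Rutgeerts.** Normal linear regression imputation on treatment group, 185 per arm, 15% missing completely at random, was simulated. Recurrence among imputed participants, placebo / guselkumab:

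| Shares | Unrounded, ≥ 2 | Rounded to a grade |
|---|---|---|
| A | 46.9% / 31.2% | 59.7% / 43.4% |
| B | 37.3% / 23.3% | 54.0% / 38.1% |
| C | 49.9% / 35.1% | 60.1% / 44.9% |
| D | 34.4% / 20.4% | 51.3% / 34.6% |

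Against 50% / 30%, the error among imputed participants runs from near zero to about 16 points. The difference among them is 14.0 to 16.7 points. The overall difference is 0.85 × 20 + 0.15 × (imputed difference), which is 0.85 × 20 + 0.15 × 14.0 = 19.1 at the low end and 0.85 × 20 + 0.15 × 16.7 = 19.5 at the high end. The loss is therefore 0.5 to 0.9 points out of 20.

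**Step 3: AP-free, unbounded draws.** None of the imputed participants is AP-free, so the analysed rate is (1 − m) × true rate at missing fraction m.

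| m | Analysed rates | Power, n = 185 |
|---|---|---|
| 0 | 40.0% / 55.0% | 82.6% |
| 5% | 38.0% / 52.3% | 78.9% |
| 10% | 36.0% / 49.5% | 74.9% |
| 15% | 34.0% / 46.8% | 70.7% |
| 20% | 32.0% / 44.0% | 66.3% |

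Part of this drop comes from the missing data alone. Correct MAR imputation with uninformative covariates recovers the rates but roughly the precision of the observed cases: 185 × 0.85 ≈ 157 per arm at 40% v 55% gives s0 = 0.0564, s1 = 0.0557, z = 0.709, power 76.1%. At 15% missing, then, about 82.6 − 76.1 = 6.5 points would be lost under any valid MAR method, and about 76.1 − 70.7 = 5.4 points are due to the misfit.

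**Step 4: AP-free with a repair the SAP does not state.** In the same type of simulation, a floor at 0 makes about 19% / 28% of imputed participants AP-free, and rounding to the nearest 1/7 makes about 23% / 32%, both below 40% / 55%. Rounding to a whole number overshoots instead, at about 48% / 59%. None of these choices returns the assumed rates.

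**Step 5: other analyses.** The tipping-point analysis (5.3.5.1) varies the binary recurrence status directly, and the supplementary estimand (5.3.3.2.1) counts missing status as recurrence. Neither uses Table 8, and both cover the primary endpoint only.

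**The case against.** The strongest reply is that this is missing detail and not a wrong method. The SAP does not say linear, unrounded or unbounded, and a programmer would probably add a floor or round. That is fair as to wording, and it rules out saying that AP-free imputations are impossible under the plan. It does not rescue the method, because the usual repairs also miss the assumed rates, in a direction set by the rounding unit.

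Other points stand:
- For raw draws, the AP result is non-responder imputation, which SAP 5.5.2 itself adopts for its other binary endpoints. It shrinks the difference (15 to 12.75 points at 15% missing) and costs power, but does not favour guselkumab.
- Missingness of 15% is towards the upper end. The dropout rate is stated for the time-to-event calculation, participants with ICEs 1–4 are already scored as failures, and protocol 4.1 asks for an early termination visit with ileocolonoscopy.

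A reader might infer two stronger claims. One is that the primary result would be wrong; Step 2 shows a shift of under 1 point, on assumed distributions. The other is survivor bias: that the Rutgeerts model learns only from participants who did not fail before Week 48. The documents do not support this as a general statement. Protocol 6.8.1 keeps participants who start rescue medication in follow-up, and 6.5.1 allows those with Week 24 endoscopic recurrence to remain on assigned treatment, so some early failures can have Week 48 grades. Taking the full 50% / 30% as the target for every missing participant also treats all of them as lost at Week 0, whereas later dropouts have already passed part of the risk period.

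**Conclusion.** The concern holds as a defect of specification. A continuous model is named for an ordinal grade with no stated coding, and for a score judged against exactly 0.

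For the primary endpoint the consequence is an avoidable choice left to the programmer, worth 0.5 to 0.9 points of a 20-point difference at 15% missing, with two analyses that bypass the model. For AP-free, the stated MAR imputation is not what the method delivers. At 15% missing and assumed rates of 40% v 55%, power is about 71%, against about 76% under a well-specified imputation and about 83% with complete data, and no sensitivity analysis would reveal it.

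These sizes rest on assumed grade and AP distributions, on data missing completely at random, and on imputation from treatment group alone. The sample size and stated power do not change. Because the trial stopped after four enrolments, the point concerns the plan as a reference text and not any reported finding.

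**What to change.** 1. In Tables 8 and 12, apply the ICE rules first and then impute the binary status: recurrence yes/no, and AP = 0 yes/no, by logistic regression. For Rutgeerts, an ordinal model for the grade, with the grade order written out, is an acceptable alternative.
2. Use the listed covariates that are actually collected. Remove baseline Rutgeerts score from Tables 11 to 13, since no baseline ileocolonoscopy is scheduled.
3. Correct the narrative in 5.4.1.3 so that each endpoint names the variable its table imputes. Clinical remission without disease recurrence depends on both CDAI and the Rutgeerts grade, so its entry should say how each is filled in.
4. Do not simply pool all early failures into the fitting data for the primary model. Without conditioning on time of dropout, that would over-impute recurrence in participants known to be failure-free when they were lost.

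The cost is a rewrite of the four imputation tables and their text, with no new data and no change to sample size. It matters if this SAP is reused as a template.
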